**Access to clinical care at MRCG**

The mother and baby will be entitled to receive care at the MRC Gambia Clinical Services Department for the first 28d of the baby's life. As there is no neonatal unit at this hospital the neonate will not be transferred to receive care here, but following discharge the mother may wish to access the health service if she or her baby develops complications. This is standard MRC Gambia practice for study participants. In addition, if a study participant requires any tests that are not available at the study site, they will be able to access them through the MRCG Clinical Services and facilitated by the study team.

**14.3.2.b Benefits for health-care system**

In the long-term the introduction of continuous KMC will benefit the study site hospital (EFSTH) by reducing the work load for neonatal staff; promoting early discharge and reducing the burden of neonatal unit over-crowding; continuing professional development of neonatal unit staff with KMC training and development of protocols to guide the management of preterm/LBW neonates.

The storage and future analysis of environmental and invasive isolates will provide important information about the epidemiology of hospital acquired infections in this population and may provide a platform for future research in this area. The antibiotic sensitivity profile of gram-negative bacilli will contribute towards the understanding of local antibiotic resistance patterns and the development of local and national anti-microbial prescribing policies.

**14.4 Sensitisation**

It is not feasible to conduct individual sensitisation or antenatal consent for this study as it is not possible in the local context to identify which pregnant women will give birth to a preterm/LBW baby. However, group sensitisation of expectant mothers and families at "high-risk" antenatal clinics at the major referral sites will take place prior to and through-out the study to educate potential families about the study, the recommendation for KMC in stable babies and the KMC unit. Following admission of the baby to the neonatal unit, parent or caregiver will be sensitised about the study and verbally invited to participate. If they agree, they will undergo the consent process. Details of any sensitisation will be recorded on the eCRF

**14.5 Informed consent**

**14.5.1 Background to informed consent process**

There are recognised challenges in obtaining parental consent in neonatal research involving sick newborns with a time limited intervention in resource limited settings. Alternative approaches include parental assent with later full consent or, if locally acceptable, consent from an alternative relative who is present with the baby and has permission to provide consent on the parents behalf.

**14.5.2 Informed consent for neonatal participation**

*Timing of consent*

Written, informed consent will take place as soon as possible following screening procedures and prior to randomisation.

*Content of informed consent*

Informed consent will be taken for the following: neonatal inclusion in the study; randomisation and receipt of the intervention; provision of continuous skin-to-skin contact if allocated to the intervention arm; collection of socio-demographic data; collection of clinical data; collection of biological samples and follow-up.

Protocol #: 1

*Person providing informed consent on behalf of the subject*

[figure not shown]
The preferred person to provide informed consent is the parent, but it is recognised that this may not be possible within the time-frame, as outlined in section 14.5.1. If the parent is not available within defined time points (figure 3), it will be explored if there is any relative available. The relative, or caregiver, will then consent on the parents behalf, obtaining verbal permission from the parents via telephone contact if the caregiver wishes. A Statement of Guardianship form will be completed to document the details and relationship of the guardian to the baby. Once the parent is available at the study site, parental informed consent will be obtained to ensure that they agree for the baby to continue in the study.

**14.5.3 Informed consent for maternal swabs/caregiver swabs**

Written informed consent for obtaining maternal/caregiver swabs will be taken after consent for the neonates participation but prior to any maternal/caregiver samples being obtained. All participants will have the option of declining to have a particular swab taken (E.g. recto-vaginal) if they are not comfortable with the procedure.

Within the intervention arm, consent will be taken from the person providing initial KMC, which is expected to be the mother in most cases but may be another female family member or the father. If the mother later becomes available to provide KMC, she will be asked to provide informed consent for repeat swab samples at time of commencing skin-to-skin contact.

Figure 3. Flow chart for obtaining informed consent for neonatal participation in eKMC study

Protocol #: 1

---

Obtaining the maternal/caregiver samples will not delay starting the intervention. For subjects allocated to the control group, informed consent for swab samples will be taken from the mother or caregiver prior to the subject receiving any skin-to-skin contact (table 3).

Table 3. Outline of consent process for mothers/caregivers providing biological samples

Study arm	Scenario	Consent taken from	Purpose of consent	Timing
Intervention	Mother present at time of recruitment	Mother	Recto-vaginal swabs Skin swabs	Before commencing intervention
	Another caregiver present at time of recruitment (E.g. Father/aunty/grandmother)	Caregiver who is present & providing skin-to-skin contact	Skin swabs	
		Mother once available	Recto-vaginal swabs Skin swabs	prior to starting skin-to-skin contact
Control	Mother present at time of recruitment	Mother	Recto-vaginal swabs Skin swabs	Before commencing any skin-to-skin contact
	Another caregiver present at time of recruitment (E.g. Father/aunty/grandmother)	No consent for biological samples taken. Wait for mother to be present or baby ready to start skin-to-skin contact with person other than mother	Skin swab	Before commencing any skin-to-skin contact
		Mother once available	Recto-vaginal swab Skin swab	As soon as possible after mother available and prior to starting any skin-to-skin contact

#### **14.5.4 Special consent situations**

If the mother of the baby is aged <18y old, she can still provide full informed consent, as per MRC Gambia SOP-CTS-015 section 4.8.7. If the caregiver has impaired mental capacity an alternative caregiver will be sought to provide consent instead. This could be the father of the baby or a trusted family member such as an aunty or grandmother.

#### **14.5.5 General process of informed consent procedure**

Study personnel will have undergone detailed training about informed consent procedures and only trained study personnel will take informed consent. All consent procedures will take place in a private, quiet area and every effort will be made to perform the informed consent process in a sensitive manner. Consent should not be taken on the neonatal unit, in-order to avoid distraction or distress to the caregiver.

Protocol #: 1

---

The information sheet will be provided to the caregiver to read in English. If the care-giver is unable to read, the information sheet will be read out-loud in the presence of a literate and impartial witness, as per ICH-GCP guidance. Independent, impartial witnesses will be identified prior to the study starting and their curriculum vitae kept in the study file. They will be re-imbursed for expenses, in accordance with MRCG policy. If the caregiver does not speak English, the study personnel will translate the content of the information sheet into the language of understanding as applicable, as per standard practice at MRC.

The parent/caregiver will have the opportunity to have all questions answered before being asked to sign or thumb-print on the consent form. Written informed consent will be taken using the study information sheets and consent forms and all signed consent forms will be kept in a file in the locked study office at the study site for the duration of the study and later archived at MRCG with other study documents. Either a certified copy of the signed consent form or a second, signed form, will be given to the parent/caregiver. The research nurse or clinician will document that informed consent has been taken in the source medical record of the participant. A Statement of Guardianship form will be completed for all people giving consent who are not the parents of the participant.

If any photographs are taken involving study participants, informed consent will be taken prior to obtaining the image. This will be written consent, recorded on the MRCG Photographic consent form. Consent will be taken for use of the image in presentations, sensitisation and educational activities related to the research.

#### **14.6 Participant confidentiality**

Confidentiality will be ensured by the use of non-identifiable unique study numbers and exclusion of all subject identifiable information from the study database. The unique study number will be in the format N000. All paper and electronic data collection forms, laboratory forms, reports and administrative forms will include the study number and at least one other identifying detail (E.g. randomisation number, screening number, date of birth) As data will be collected on multiple occasions, a mastersheet linking the subject identifying information and the unique study number will be used to enable collection of data by different personnel at different time-points. The paired mother/caregiver will be allocated a unique study number in the format CG000 in a consecutive order. The caregiver enrolment log sheet will document the paired neonatal study number for each participant so that maternal/caregiver-neonatal dyads can be identified. The contact information will be kept within the participant folder and all forms will be kept in the locked study office at the study site.

#### **15 FUTURE USE OF STORED SPECIMENS**

All isolates identified from neonatal blood and CSF culture will be stored for future molecular characterisation and comparison with carriage and environmental isolates. All neonatal, maternal and environmental swab samples will be stored for future microbiological (culture, antibiotic sensitivity testing and ESBL detection) and molecular analysis (including 16SrRNA and whole genome sequencing), dependent on additional funding

#### **16 FINANCING AND INSURANCE**

This project is funded through a Wellcome Trust Research Training Fellowship to the PI and there is sufficient funding available for the study. Additional funding will be sought for future microbiological and molecular analysis of stored samples. London School of Hygiene & Tropical Medicine holds Public Liability ("negligent harm") and Clinical Trial ("non-negligent harm") insurance policies which apply to this trial.

Protocol #: 1

---

## 17 PUBLICATION / DISSEMINATION POLICY

The results of this study will be published in peer-reviewed scientific journals and as part of the PI's PhD thesis, through which potential users of the data will become aware of the data set.

The datasets collected will be available to other users once all relevant trial related publications in scientific journals have been accepted. Requests for access to the complete dataset will be reviewed by the Scientific Coordinating Committee of MRC Unit The Gambia and The Gambian Government/MRC Joint Ethics Committee to establish the validity of the request. The study documents and dataset will also be made available on LSHTM Data Compass repository.

The results will be made available to open-access databases once peer-reviewed publications have been accepted. Local stakeholders will be informed of key results at an appropriate time following completion of the study.

## APPENDIX I. SCHEDULE OF RECRUITMENT ACTIVITIES

[figure not shown]
Activity	Tasks/method	Staff member	Documentation	Estimated time *
Identify potential participants	Screen all new admissions to EFSTH NNU to identify those with weight <2000g	MRC research nurse EFSTH nurse	Admission log	5 minutes
Sensitisation	Inform available parents/caregivers of potential participants about the study and screening procedures	MRC research nurse	eCRF	10 minutes
Screening for clinical eligibility	
 
✓ Check age from source documents
 
✓ Weigh on study scale
 
✓ Examination
 
✓ Continuous pulse oximetry for 3h and manual recording of RR and breathing over 10 minute period at 00:00 & 02:50
 
✓ Take temperature / blood glucose to aid clinical management
 
	MRC research nurse	
 
1. Screening log
 
2. Eligibility checklist with criteria
 
3. Screening Clinical Assessment Form
 
	20 minutes  10 minutes OR 2h 50 minutes
Informed consent	Informed consent for eligible babies: 
 
- Consent for baby to participate in RCT
 
- Consent to providing intervention if randomised to that arm
 
	MRC research nurse/research Clinician	Information sheets & consent forms	40 minutes – 3h
Enrolment	Allocate unique study ID number to neonate and parent/caregiver	MRC research nurse	Enrolment logs	5 minutes
Collection of baseline data	✓ Auxiliary temperature	MRC research nurse	1. Clinical assessment form	30 minutes
	✓ Blood glucose		2. Biological samples log sheet	10 – 30 minutes
	✓ Head circumference & length measurement		3. Transport log sheet	
	✓ Neonatal rectal, skin, & nasal swabs			
	✓ Maternal/caregiver paired swab samples (within 24h)		eCRF	60 minutes (as soon as possible)
Randomisation & allocation	Randomised & allocated to intervention or control arm	Research clinician	Randomisation log	10 minutes

\* Screening, and enrolment activities are estimated to take between 2hr 20 minutes and 6h 10 minutes to complete (not including collection of socio-demographic data). If the informed consent process is delayed for any reason, this may be extended but the baby will be ineligible if no consent within 24h of admission.

Protocol #: 1

## APPENDIX II. NEW BALLARD SCORE FOR ASSESSING GESTATIONAL AGE

### Neuromuscular Maturity

Score	-1	0	1	2	3	4	5
Posture							
Square window (wrist)	 > 90°	 90°	 60°	 45°	 30°	 0°	
Arm recoil		 180°	 140–180°	 110–140°	 90–110°	 < 90°	
Popliteal angle	 180°	 160°	 140°	 120°	 100°	 90°	 < 90°
Scarf sign							
Heel to ear							

### Physical Maturity

Skin	Sticky, friable, transparent	Gelatinous, red, translucent	Smooth, pink; visible veins	Superficial peeling and/or rash; few veins	Cracking, pale areas; rare veins	Parchment, deep cracking; no vessels	Leathery, cracked, wrinkled
Lanugo	None	Sparse	Abundant	Thinning	Bald areas	Mostly bald	
Plantar surface	Heel-toe 40–50 mm: -1 < 40 mm: -2	> 50 mm, no crease	Faint red marks	Anterior transverse crease only	Creases anterior 2/3	Creases over entire sole	
Breast	Imperceptible	Barely perceptible	Flat areola, no bud	Stippled areola, 1–2 mm bud	Raised areola, 3–4 mm bud	Full areola, 5–10 mm bud	
Eye/Ear	Lids fused loosely: -1 tightly: -2	Lids open; pinna flat; stays folded	Slightly curved pinna; soft, slow recoil	Well curved pinna; soft but ready recoil	Formed and firm, instant recoil	Thick cartilage, ear stiff	
Genitals (male)	Scrotum flat, smooth	Scrotum empty, faint rugae	Testes in upper canal, rare rugae	Testes descending, few rugae	Testes down, good rugae	Testes pendulous, deep rugae	
Genitals (female)	Clitoris prominent, small labia minora	Clitoris prominent, enlarging minora	Majora and minora equally prominent	Majora large, minora small	Majora cover clitoris and minora		

Score	Weeks
-10	20
-5	22
0	24
5	26
10	28
15	30
20	32
25	34
30	36
35	38
40	40
45	42
50	44

Protocol #: 1

### APPENDIX III: ADAPTED SCRIP SCORE FOR MEASUREMENT OF CARDIO-RESPIRATORY STABILITY OUTCOME

		2 points	1 point	0 points
A	Cardiovascular stability:  Heart rate (beats per minute)	120 – 160 for 10 mins continuously	100 - 120 or 161 – 200 for >5 out of 10 mins	<100 or >200 continuously for >5 out of 10 mins
B	Respiratory stability:  Breathing pattern and respiratory rate (RR) (breaths per minute)	Regular breathing  And/or  RR 20 – 60 continuously for 10 mins	Irregular or periodic breathing with 1 or more pauses for <10 secs  And / or  RR 20 – 29 or 61 – 100 for >5 out of 10 mins	Irregular breathing with 1 or more pauses for >10 secs  And / or  Irregular breathing with 1 or more pauses for <10 seconds but which result in oxygen saturation <88%  Need for bag-valve-mask ventilation  And / or  RR <20 or >100 for >5 out of 10 mins
C	Oxygen saturation (%)	>88% continuously in room air for 10 mins	>88% continuously for >5 out of 10 mins in oxygen	<88% continuously for >5 out of 10 mins despite oxygen

[figure not shown]
Stable = 6

Mild – moderately unstable = 3 – 5

Severely unstable = 0 - 2

Protocol #: 1

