### **6.3 Missing data**

The amount of missing data is expected to be low (<5%) and a complete case analysis will be conducted.

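### As far as it can be read, the Appendix III aSCRIP table gives some records two scores and others none, and the SAP adds no rule for scoring secondary outcome 2

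*Protocol*

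**What the plan says.** Mean aSCRIP at 24 hours is secondary outcome 2 (Protocol 2.2; SAP 6.1). Cardio-respiratory stability at 24 hours is the only outcome listed under Objective 3, the safety objective (Protocol 2.1). Protocol 6.1.1 has the score calculated post hoc, by reference to Appendix III.

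Appendix III scores three rows 2, 1 or 0 and adds them:

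- **Heart rate.** 2 points: "120 – 160 for 10 mins continuously". 1 point: 100 to 120 or 161 to 200 for more than five of ten minutes. 0 points: below 100 or above 200 for more than five.
- **Respiration.** 2 points: regular breathing and/or "RR 20 – 60 continuously for 10 mins". 1 point: pauses shorter than 10 seconds and/or "RR 20 – 29 or 61 – 100 for >5 out of 10 mins". 0 points include "Irregular breathing with 1 or more pauses for >10 secs" as one trigger among several.
- **Saturation.** 2 points: ">88% continuously in room air for 10 mins". 1 point: ">88% continuously for >5 out of 10 mins in oxygen". 0 points: below 88% for more than five minutes despite oxygen.

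A total of 6 is stable, the next band is "Mild – moderately unstable = 3 – 5", and 0 to 2 is severely unstable.

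The SAP names the score (3.6, 6.1) and compares continuous outcomes with random effects models (6.2), but gives no scoring rule. For missing data, SAP 6.3 states that "a complete case analysis will be conducted".

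**The concern.** A score that enters a comparison of means must give each record exactly one value. Here some records satisfy two or three cells of a row and others satisfy none, so two analysts following the table faithfully could produce different datasets for the same outcome. The affected outcome is the only one listed under the safety objective. The rule that resolves these cases should be on paper before the arms are compared.

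**Working it through.** No sample size or power figure is involved. The check reads each cell literally and asks how many cells a ten-minute record meets.

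**Overlaps**

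1. *Rate 20 to 29.* Every whole-number rate from 20 to 29, held for ten minutes, meets both the 2-point and the 1-point rate conditions. Take heart rate 140, room air above 88% throughout, and regular breathing at 25. The total (heart rate + respiration + saturation) is 2 + 2 + 2 = 6 or 2 + 1 + 2 = 5. The Definitions section lists 20 to 60 as the stable respiratory range, yet on one reading this baby misses the stable total.
2. *The and/or join.* Rate 40 with one 12-second pause meets the 2-point cell through its rate and the 0-point cell through its pause. With heart rate 140 in room air above 88%, the total is 2 + 2 + 2 = 6 or 2 + 0 + 2 = 4. With heart rate 110 in oxygen above 88%, it is 1 + 2 + 1 = 4 or 1 + 0 + 1 = 2, which crosses into the severely unstable band. Rate 25 with a pause above 10 seconds meets all three cells.
3. *Heart rate 120.* The value is printed in both the 2-point and 1-point cells. The overlap needs a trace within 120 to 160 throughout, with more than five minutes at exactly 120. That is 5 of the 3003 ways of dividing ten minutes among six heart-rate bands, so it is minor.

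**Gaps on a literal reading**

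| Record | Cell met |
|---|---|
| Room air, below 88% for all ten minutes | none |
| Room air, above 88% for 9 minutes and below for 1 | none |
| Heart rate 140 for 8 minutes, 170 for 2 | none |
| Exactly 88% throughout, in air or oxygen | none |
| In oxygen, 5 minutes above 88% and 5 below | none |
| In oxygen, above 88% in minutes 1–5 and 7–10, below in minute 6 | 1 point if minutes are added; none if an unbroken run above five is required |

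**What the stability footnote would settle**

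The footnote to the stability summary table in the protocol's Definitions classifies saturation, heart rate and respiratory rate by the values present for at least five of ten minutes, and sends 5/5 ties to the less severe category. The table itself uses 88% or above. Carried over to aSCRIP, these conventions would settle the last five rows of the table above. They would leave three problems: the 20 to 29 overlap, the and/or conflict, and room-air saturation that is mostly below 88%.

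Saturation shows the difference. Ten minutes can be divided among above, at and below 88% in 66 ways. Read literally, 65 of 66 room-air patterns and 36 of 66 oxygen patterns meet no cell. With the footnote and the 88%-or-above cut, the oxygen gaps close. The room-air gaps fall to patterns with six or more minutes below 88%: 5 + 4 + 3 + 2 + 1 = 15 of 66. These are counts of possible patterns and say nothing about how often they occur in babies.

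**The case against.** The strongest reply is that much of the gap list is a missing cross-reference. The footnote uses the same ten-minute window and the same 88% figure, and it sits beside a stable definition that also asks for ten minutes in room air. This stands for mixed traces, ties, exactly 88% and the run-versus-total question. But the footnote is written for the stability classes, and Appendix III prints a strict above-88% threshold without referring to it.

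A second reply is that no sensible scorer would give 2 points despite a long pause, because the 0-point cell names that pause as its own trigger. That is probably the intent. It is not written, however, and a worst-cell rule would fill none of the gaps. Protocol 6.1.1 has breathing pattern recorded by hand every six hours and does not say that pause lengths are noted, so the practical reach of this conflict is uncertain.

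Third, relevant material is out of sight: a figure in Appendix III is not shown, and the study-specific procedures and the stability measurement log (Protocol 11.1.2) are not reproduced. The point is therefore limited to the readable text.

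A reader might infer two stronger conclusions that the documents do not support:

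- *That the rule will be picked after seeing the data.* Post-hoc calculation in Protocol 6.1.1 fits with oximeter recordings being downloaded once monitoring ends (Protocol 11.1.3). The interim considered the secondary outcomes other than ESBL carriage (SAP 3.4), so some scoring may already have been in use. Protocol 3.3.2 names this outcome for blinding where possible.
- *That desaturating babies will be lost from the analysis.* Nothing says that an unmatched component is set to missing. Only if it were would the complete case analysis drop those babies.

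**Conclusion.** The concern holds for the readable text of Appendix III. The firm defects are the rate 20 to 29 overlap, the and/or conflict without precedence, and the absence of a cell for room-air saturation below 88%. The remaining gaps depend on whether the stability footnote applies, and the heart-rate 120 overlap is a boundary detail.

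For a single record, the overlaps move the total by 1 or 2 of 6 points and can change its band. How many babies are affected, and whether the number differs by arm, cannot be derived from the documents, so a reader should not infer bias in the treatment comparison. The reach is one of eight secondary outcomes. The primary outcome, the heart-rate and saturation analysis in SAP 6.4.1 and the harms analyses in SAP 6.5 do not use this table. The conclusion assumes that the figure not shown holds no scoring rule.

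**What to change.** Before database closure and any analysis, the point SAP 3.5 sets for posting the plan, put one reconciled aSCRIP table in the SAP that:

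- removes the overlaps at respiratory rate 20 to 29 and heart rate 120;
- states one order of precedence when a record meets two cells;
- assigns a score to room-air saturation at or below 88%;
- states whether the stability footnote (at least five of ten minutes, ties to the less severe category, 88% or above) governs aSCRIP.

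If a note in the figure not shown already gives the rule, copy it into the SAP. State any rule used at the interim, and score without knowledge of arm where possible, in line with Protocol 3.3.2.

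The cost is one table. Heart rate and saturation can be rescored from stored oximeter data (Protocol 11.1.3). Respiratory rate and breathing pattern can be scored only from what was written down, so the table must fit those records. The change concerns outcome scoring only and alters no eligibility, stopping or treatment criterion.
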